#### **Count-data secondary endpoints:**

The analyses of the following secondary endpoints will be performed both for the in-study and on-treatment observation period, in the same way as the analysis of the primary endpoint:

- Number of AEs
- Number of SAEs
- Number of medication errors (incorrect dose administration rate)

#### **Continuous secondary endpoints:**

For the following secondary endpoints, the change will be estimated by length of follow-up and by treatment duration. Patients on oral oestrogen therapy and patients with childhood-onset GHD will be addressed in stratified analyses. The effect of a previous GH replacement therapy on the health-related quality of life will be checked in stratified analyses.

- Change in IGF-I SDS
- Change in weight
- Change in BMI
- Change in waist circumference
- Change in waist-hip ratio
- Change in lipid profile
- Change in HbA1C
- Change in bone density
- Change in bone mineral content
- Change in total body fat mass
- Change in truncal fat mass
- Change in lean body mass
- Change in body fat percentage
- Change in VAT
- Change in liver function
- Change in PRO score (TRIM-AGHD)

Protocol  
 Study ID: NN8640-4515  
 UTN: U1111-1264-8642  
 EU PAS No: Pending

**CONFIDENTIAL**

Date: 15 February 2022  
 Version: 3.0  
 Status: Final  
 Page: 31 of 53

**Novo Nordisk**

### **Categorical secondary endpoints:**

The binary categorisation of the endpoints Patient achieving IGF-I SDS target (0 -+2) and Patient reaching satisfactory clinical response will be used to calculate the proportion (%) of patients achieving these criteria.

#### **9.7.2.3 Analysis of exploratory endpoint(s)**

The number of sick days and physician visits in the AGHD WSI will be converted into visits per year. The impact on productivity and ability to do regular activities will be analysed in the same way as the secondary endpoint Change in PRO score (TRIM-AGHD).

The number of anti-diabetic medications will be presented in descriptive tables for the subgroup of patients with diabetes mellitus type 2 at baseline by length of follow-up and by treatment duration.

#### **9.7.3 Interim analysis**

The interim reports are planned with data cut at 3 and 6 years after PPFV respectively and will include the same analytic approach as the final report.

#### **9.7.4 Sequential safety analysis/safety monitoring**

Events listed in the endpoints will be reported as SAEs, ARs and AEs, and summarized separately by statistical analysis.

### **9.8 Quality control**

#### **9.8.1 Monitoring procedures**

During the course of the study, monitoring should be performed to ensure that the protocol has been adhered to. The extent of source data verification and validation of endpoints will be described in the CRA monitoring plan.

#### **9.8.2 Critical documents**

Before the physician starts the study (which is when informed consent is obtained from the first patient), the following documents must be available to Novo Nordisk:

- Regulatory approval and/or notification as required
- Documentation of the physician's qualifications as medically qualified (for instance a short CV or authorisation)
- Signed and dated agreement on the final protocol
- Approval/favourable opinion from Institutional Review Board (IRB)/Independent Ethics Committee (IEC) (or other appropriate bodies as required locally) clearly identifying the documents reviewed: the protocol including version, patient information/informed consent form and any other written information to be provided to the patient, patient enrolment procedures
- Copy of IEC/IRB approved patient information/informed consent form/any other written information/advertisement (or document of waiver by IEC/IRB of informed consent)
- Non-interventional study agreement

Protocol  
 Study ID: NN8640-4515  
 UTN: U1111-1264-8642  
 EU PAS No: Pending

CONFIDENTIAL

Date:	15 February 2022	Novo Nordisk
Version:	3.0	
Status:	Final	
Page:	32 of 53	

### 9.8.3 Retention of study documentation

Novo Nordisk will comply with Good Pharmacoepidemiology Practice (GPP) and relevant national legislation related to archiving of study documentation.

The physician must agree to archive the documentation pertaining to the study in an archive for 5 years after final report/first publication of the study, whichever comes later. The physician should not destroy any documents without prior permission from Novo Nordisk

Novo Nordisk will retain the documentation pertaining to the study according to company procedure and in accordance with national regulations if they require a longer retention period.

### 9.9 Limitations of the research methods

As this is a non-interventional study, data collection will reflect routine clinical practice rather than mandatory assessments at pre-specified time points, which may have an impact on the amount of data and its interpretation.

AGHD is characterised by low prevalence, resulting in the need to capture data from many different regions and settings. In addition to the non-interventional nature of the study, this leads to a potentially heterogeneous patient population and different local standard of care and data capture, e.g., local differences in diagnostics, laboratory analyses, and reporting of events. This could result in a risk of information bias.

In any non-interventional study, there is a risk of selection bias, affected by the willingness and/or ability of physicians and patients to participate in the study. In addition, any undiagnosed patients will not be able to participate, and the rate of underdiagnosis may vary between regions. This may lead to a selected patient population, which does not accurately reflect the underlying patient population and may result in limited data on certain subgroups.

The long-term follow-up is a strength of this non-interventional study, but also leads to a risk of loss to follow up.

As with any observational study, there is potential for bias resulting from variable quality and completeness in the information on potential confounders. Age, gender, previous GH treatment and medical history are among the potential confounders, and information on these will be collected to the extent possible. However, potential unmeasured confounding factors cannot be ruled out.

Considering that AGHD is a rare disease, the inclusion of Nordinet® IOS historical comparison group will provide an unique opportunity to evaluate the long-term safety, including the detection of rare adverse events, as well as the clinical parameters of GH replacement therapy across a heterogeneous patient population. Furthermore, patient data in this Sogroya® (somapacitan) prospective NIS (present study) and Nordinet® IOS historical comparison group are considered to be comparable, as natural history of the disease or the management of AGHD, i.e., diagnostic criteria and treatment options over the past 10 years (time-course of data collection in the Nordinet® IOS) has not changed significantly. However, the proposed historical comparator is a finalised non-interventional study and therefore has the same potential limitations as mentioned above. The comparability between the results of the two studies and any limitations in the conclusions will therefore be thoroughly discussed in the final study report.

Protocol  
 Study ID: NN8640-4515  
 UTN: U1111-1264-8642  
 EU PAS No: Pending

~~CONFIDENTIAL~~

Date:	15 February 2022	Novo Nordisk
Version:	3.0	
Status:	Final	
Page:	33 of 53	

## 9.10 Other aspects

Not applicable section, as all aspects of the study is covered by the previous sections.

## 10 Protection of human subjects

The study will be conducted in accordance with GPP, applicable regulatory requirements and in accordance with the declaration of Helsinki.

### 10.1 Informed consent form for study patients

A voluntary, signed and personally dated informed consent form will be obtained from the patient prior to any study-related activity.

The physician must give the patient information in a form that the patient can read and understand. This includes the use of impartial witness where required.

In obtaining and documenting informed consent, the physician must comply with the applicable regulatory requirement(s) and adhere to the requirements in the Declaration of Helsinki.

The task of seeking informed consent can only be performed by the physician or another medically qualified person delegated by the physician, if permitted by local regulation, who must sign and date the patient information/informed consent form.

### 10.2 Data handling

If the patient withdraws the previously given informed consent, the patient's data will be handled as follows:

- Data collected will be used as part of the statistical analysis
- Safety events will be reported to Global Safety, Novo Nordisk/health authorities.

Data will be collected and handled in accordance with local law and IRB/IEC procedures.

### 10.3 Institutional Review Boards/Independent Ethics Committee, health authorities and other relevant national institutions/bodies

Study specific documentation (for example study protocol, Patient Information/Informed Consent Form, patient materials) must be submitted to the relevant national bodies as required by national regulation and procedures in the participating countries.

The study must be approved by the IEC/IRB for each participating country and/or other appropriate bodies as required locally.

In accordance with regulatory requirements, including GVP, the sponsor will inform the health authorities of Sogroya® (somapacitan) ADRs. In certain situations, other adverse events may be subject to expedited reporting, if required by health authorities. In addition, Novo Nordisk will inform the IECs/IRBs (or other appropriate bodies as required locally) of Sogroya® (somapacitan) related serious adverse reactions, in accordance with the local requirements in force.

Protocol  
 Study ID: NN8640-4515  
 UTN: U1111-1264-8642  
 EU PAS No: Pending

~~CONFIDENTIAL~~

Date:	15 February 2022	Novo Nordisk
Version:	3.0	
Status:	Final	
Page:	34 of 53	

## 10.4 Premature termination of the study

The sponsor may decide to stop the study or part of the study at any time. However, the study may only be terminated prematurely after consultation and in agreement with relevant regulatory authorities.

If a study is prematurely terminated or suspended, information must be provided to the relevant national bodies as required by national regulation and procedures.

# 11 Management and reporting of adverse events/adverse reactions

## 11.1 Collection of adverse events and other safety information

Safety definitions and a guideline for evaluation of outcome, severity and causality can be found in [Appendix A](#).

All adverse events including all fatal outcomes on Sogroya® (somapacitan) which occur after informed consent is obtained and until the end of study for each participating patient must be collected and reported to Novo Nordisk.

If the physician becomes aware of events of overdose, abuse, misuse, medication errors, lack of therapeutic effect or occupational exposure related to the study product treatment with or without an associated suspected adverse reaction, this should be reported to Novo Nordisk on the NIS Safety Form and on the medication error, misuse and abuse form (misadministration). These events will be summarised by Novo Nordisk in the interim and final study reports.

For female patients: Pregnancies and pregnancy outcome should be collected including **adverse events** in the pregnant patient, foetus or newborn infant from birth to 12 months of age.

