**Figure 1 Study Design**

**Note:** symbol (  ) Represents interim reporting

The study is planned to collect a broad variety of safety and other clinical parameters data generated during routine clinical care visits and other relevant clinical contacts (e.g. phone calls between patient and clinical site) in AGHD patients treated with commercially available Sogroya® (somapacitan). The duration of the study is planned with patient participation for 5 years or longer up to a total study duration of 10 years, if possible. The main purpose of the study is to observe patients for long-term safety. It is however well known that adult patients on GH therapy, often interrupt or discontinue treatment. Due to this expected dropout from treatment, and in the context of the duration of the study, patients switching from or discontinuing treatment with Sogroya® (somapacitan) will be offered continuation in the study in order to collect post treatment data.

The current study will compare data from a non-interventional registry study (NordiNet® IOS) which was monitoring the long-term use of once daily Norditropin® as a historical comparison group consisting of approximately 2300 AGHD patients enrolled in Europe between 2006 and 2016.

The sample size estimation for this study is based on the incidences for neoplasms reported in Nordinet® IOS. It is estimated that a sample size of 400 patients will be required to rule out the doubling of incidence for neoplasms in patients treated with Sogroya® (somapacitan).

Data on concomitant medication, medical history (adult/ childhood onset of GHD), laboratory parameters including but not limited to hepatic, renal, heart and diabetes status as well as data on neoplasms and medication errors will be collected as part of this study if available per routine clinical practice in order to evaluate safety. Other data which are already available in the medical records or being obtained as part of routine clinical practice, such as IGF- I /IGFBP-3 values, measures of body composition and bone health and PROs, will be collected to support the evaluation of clinical parameters.

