## **9.2.7 Assessments for safety and other clinical parameters**

### **9.2.7.1 Adverse Events**

All AEs, either observed by the physician or reported by the patient following the patient’s enrolment (signing informed consent) into the study and until the end of study for each patient must be recorded and evaluated by the physician. At each contact with the site during the study, the patient should be asked about possible AEs since the last contact. Please refer to section [11](#) for AE definitions, collection, recording, and reporting.

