## 9.7 Data analysis

### 9.7.1 Definition of analysis sets

The safety analysis will be based on the Safety Analysis Set (SAS). The SAS will consist of all patients exposed to Sogroya® (somapacitan) during study period. Two observation periods are defined:

- on-treatment: from first administration until last study contact, discontinuation of Sogroya®, or withdrawal of informed consent, whichever comes first
- in-study: from first administration until last study contact, or withdrawal of informed consent, whichever comes first

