#### Adverse Event (AE)

Any untoward medical occurrence in a patient or clinical investigation subject administered/using a product and which does not necessarily have a causal relationship with this treatment. An AE can therefore be any unfavourable and unintended sign (including an abnormal laboratory finding), symptom or disease temporally associated with the use of a product, whether or not it is considered to be related to the product. An AE may be associated with the use of a drug, a medical device or both.

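### The words 'on Sogroya' in section 11.1 leave it unclear whether adverse events after stopping or switching must be reported, although sections 9.1 and 9.2.7.1 require reporting to end of study

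*Protocol*

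**What the plan says.** Five places in the Protocol bear on which adverse events a site must report.

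- **Section 11.1** is the operative instruction. It opens "All adverse events including all fatal outcomes on Sogroya" and, after the generic name, continues "which occur after informed consent is obtained and until the end of study for each participating patient must be collected and reported". One sentence therefore carries both a treatment phrase and a window that runs to end of study.
- **Section 9.2.7.1** covers all events from enrolment "and until the end of study for each patient must be recorded and evaluated by the physician". It sets no treatment condition, and it refers the site to section 11 for definitions, collection and reporting.
- **Section 9.1** says patients who stop or switch "will be offered continuation in the study in order to collect post treatment data". It runs safety monitoring from consent to the last visit, which it defines by end of study or withdrawal of consent. Stopping Sogroya is neither.
- **Section 9.7.1** defines two observation periods. One is "in-study: from first administration until last study contact, or withdrawal of informed consent, whichever comes first". The other, on-treatment, also ends at discontinuation of Sogroya.
- **Appendix A** defines an adverse event as "Any untoward medical occurrence in a patient or clinical investigation subject administered/using a product", and further on as a sign, symptom or disease "temporally associated with the use of a product, whether or not it is considered to be related to the product".

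**The concern.** Section 9.2.7.1 hands the site over to section 11 for the mechanics of reporting, so the wording of 11.1 decides whether a form is filed. Take a patient who stopped Sogroya two years ago, stayed in the study, and is now diagnosed with a neoplasm or type 2 diabetes, or dies. Under 9.1 and 9.2.7.1 the event is reportable. Under a narrow reading of 11.1 it may not be.

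The in-study evaluation is at stake. It is the secondary evaluation for adverse drug reactions (9.7.2.1) and one of two periods for adverse events, serious adverse events and medication errors (9.7.2.2). It counts time after discontinuation. If some sites leave out events from that time, the numerator is short and the denominator is not. The error goes one way, towards understating late risk, and it could differ by site or country. Section 9.1 expects adults on growth hormone to interrupt or stop often, and retains those patients in order to observe them afterwards. An analysis plan can define periods and censoring, but it cannot recover events that were never collected. The wording is therefore a matter for the protocol.

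**Working it through.** **1. The possible readings of 11.1, set against 9.2.7.1**

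| Reading of the treatment phrase | Events due after stopping under 11.1 | Agrees with 9.1 and 9.2.7.1? |
|---|---|---|
| Limits all adverse events | None | No |
| Limits fatal outcomes only | Adverse events yes; deaths after stopping not in the named set | No, for deaths |
| Has no effect | All | Yes |

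The window to end of study does not settle the matter. The treatment phrase says which events count and the window says when, so both can apply at once. Under the second reading a careful site would still capture the underlying event, because the first half of the sentence is then unrestricted. The text agrees fully with 9.2.7.1 only if the phrase is ignored.

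**2. Which results could be affected**

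- On-treatment rates: an event after discontinuation belongs to neither the numerator nor the denominator, so omitting it changes nothing. Section 9.7.2.1 makes this the primary evaluation and the one compared with NordiNet IOS.
- In-study rates: time after discontinuation is in the denominator, so an omitted event lowers the rate.

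**3. Size**

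The Protocol gives no figure for this. Its only neighbouring number is the Table 1 interval for 2% observed in 400 patients. The exact interval for 8/400 is 0.87% to 3.90%, which matches the printed 0.9 – 3.9. That interval does not enter the point.

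Let *f* be the off-treatment share of in-study person-time and *u* the share of off-treatment events not reported. With equal event rates on and off treatment:

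reported rate / true rate = (1 − f) + f(1 − u) = 1 − f·u, so the loss is f·u.

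The document gives neither *f* nor *u*. For an illustrative *f*:

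- The milestones in section 6 put first visits between 15 Dec 2022 and 15 Dec 2027 and the last visit at 15 Dec 2032. Follow-up T is then 5 to 10 years, with mean 7.5 years if entry is uniform (assumed) and nobody dies or is lost (assumed).
- Assume that 5% to 15% of patients stop per year, exponentially, and that every patient who stops stays in the study. Write λ = −ln(1 − annual stopping proportion).
- Mean of e^(−λT) = (e^(−5λ) − e^(−10λ)) / (5λ); mean on-treatment time = (1 − that mean) / λ; f = 1 − mean on-treatment time / 7.5.

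At 5% per year: λ = 0.05129; (0.77378 − 0.59874) / 0.25647 = 0.6825; (1 − 0.6825) / 0.05129 = 6.19 years; f = 1 − 6.19/7.5 = 17.5%.

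At 15% per year: λ = 0.16252; (0.44371 − 0.19687) / 0.81259 = 0.3038; (1 − 0.3038) / 0.16252 = 4.28 years; f = 1 − 4.28/7.5 = 42.9%.

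Loss of in-study events, f·u:

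| f | u = 0 | u = 25% | u = 50% | u = 100% |
|---|---|---|---|---|
| 17.5% | 0% | 4.4% | 8.7% | 17.5% |
| 42.9% | 0% | 10.7% | 21.4% | 42.9% |

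The first column is the result if sites follow 9.2.7.1. If fewer of the patients who stop remain in the study, *f* falls and so does the loss.

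**The case against.** The strongest reply is that this is one loose phrase and that the rest of the Protocol points the other way. Much of that stands.

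- The 11.1 sentence sets the same window as 9.2.7.1. A strict on-drug reading also fits badly with a window that opens at consent, since patients naïve to Sogroya can enrol and 9.7.2.1 provides a listing of reactions with onset before first dosing.
- Section 11.2 requires physicians to report serious and non-serious adverse events with no treatment condition. Section 11.3 requires an extra form for benign and malignant neoplasms and ties only medication errors, misuse and abuse to the study product. A site following these sections would report a late neoplasm.
- Section 9.1 already continues safety monitoring until end of study or withdrawal of consent, and 9.7.1 treats discontinuation of Sogroya and withdrawal of consent as separate events.

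A reader might infer that 11.1 and Appendix A together form a rule that ends reporting at the last dose. The documents do not support that. Appendix A is a general definition that does not name Sogroya and sets no cut-off at last dose. At most it is loose about patients who have stopped.

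These points make the inclusive reading the likelier intention. They do not remove the phrase from the sentence to which 9.2.7.1 sends the site, and they do not make it agree with 9.1 and 9.2.7.1.

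**Conclusion.** The point holds as a wording inconsistency with a possible, one-directional consequence. The treatment phrase in 11.1 is ambiguous and, on either limiting reading, does not match 9.1 and 9.2.7.1. A site that adopts a limiting reading could bias the in-study rates low.

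The size cannot be derived from the document. It is f·u under equal event rates on and off treatment, and 0% if sites follow 9.2.7.1. The 17.5% to 42.9% off-treatment share rests on assumed stopping rates, uniform entry, full retention of patients who stop, and no deaths or losses. Nothing in the Protocol indicates how many sites, if any, would under-report. A reader might take the upper figures as an expected loss of events, but they only bound the loss under those assumptions if no event after stopping were reported.

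Nor should a reader infer that the main safety conclusion is compromised. The primary on-treatment evaluation and the NordiNet IOS comparison do not change, and neither does the sample-size reasoning.

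**What to change.** In section 11.1, delete *on Sogroya (somapacitan)*, or replace it with *whether or not the patient is still taking Sogroya*, so that the sentence has the same scope as 9.1 and 9.2.7.1. Optionally, add one line in Appendix A stating that, for this study, the adverse event definition applies to every enrolled patient until end of study. No rewrite of 9.1 or 9.2.5 is needed.

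The cost is one phrase and, if wanted, one line. No endpoint, visit, analysis or sample size changes. The only added work is a small reporting load at any site that would otherwise have stopped reporting at discontinuation. The change should come as early as possible, because events not collected cannot be restored at analysis.
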